2.6.8. Treatment after the End of the Study**2.6.8.1. Continued Access**

After the conclusion of the study, continued access to baricitinib will not be provided. Patients will be referred to their local treatment centers for AA therapy, as clinically indicated.

2.7. Discontinuation Criteria**2.7.1. Discontinuation from Study Treatment****2.7.1.1. Permanent Discontinuation from Investigational Product**

IP should be permanently discontinued if the patient or the patient's designee requests to discontinue IP.

Discontinuation of the IP for abnormal liver tests should be considered by the investigator when a patient meets 1 of the following conditions after consultation with the Lilly-designated medical monitor:

- ALT or AST $>8 \times$ ULN
- ALT or AST $>5 \times$ ULN for more than 2 weeks
- ALT or AST $>3 \times$ ULN and TBL $>2 \times$ ULN or international normalized ratio >1.5
- ALT or AST $>3 \times$ ULN with the appearance of fatigue, nausea, vomiting, right upper-quadrant pain or tenderness, fever, rash, and/or eosinophilia ($>5\%$)
- ALP $>3 \times$ ULN
- ALP $>2.5 \times$ ULN and TBL $>2 \times$ ULN
- ALP $>2.5 \times$ ULN with the appearance of fatigue, nausea, vomiting, right quadrant pain or tenderness, fever, rash, and/or eosinophilia ($>5\%$)

NOTE: Patients who are discontinued from IP due to a hepatic event or liver test abnormality should have additional hepatic safety data collected via the hepatic safety eCRF.

IP should be permanently discontinued if any of the following are observed:

- white blood cell count <1000 cells/ μL ($1.00 \times 10^3/\mu\text{L}$ or 1.00 GI/L)
- absolute neutrophil count <500 cells/ μL ($0.50 \times 10^3/\mu\text{L}$ or 0.50 GI/L)
- lymphocyte count <200 cells/ μL ($0.20 \times 10^3/\mu\text{L}$ or 0.20 GI/L), and
- hemoglobin <6.5 g/dL (<65.0 g/L).

NOTE: Temporary interruption rules (see Section 2.7.1.2) must be followed, where applicable. For laboratory values that meet permanent discontinuation thresholds, IP should be discontinued. However, if, in the opinion of the investigator, the laboratory abnormality is due to intercurrent illness, such as cholelithiasis or another identified factor, laboratory tests may be repeated. Only when the laboratory value meets resumption thresholds (Table JAHO.2) following the resolution of the intercurrent illness or other identified factor, may the investigator restart IP, after consultation with the Lilly-designated medical monitor.

In addition, patients will be discontinued from IP in the following circumstances:

- pregnancy
- malignancy (except for successfully treated basal or squamous cell skin carcinoma)
- HBV DNA is detected with a value above limit of quantitation (see Section 9.4.8 of the JAHO(e) protocol).
- certain prohibited medications are taken per Section 2.6.7.2 (Prohibited Medications and Procedures)
- development of a VTE

Note: Patients who develop a VTE may have additional follow-up and testing recommended (see Section 9.4.9 and Appendix 7 of JAHO(e)).

If a patient develops multiple risk factors for a VTE during the conduct of the study, as described in exclusion criterion [16], the investigator may consider study discontinuation if he/she believes the risk outweighs the benefits of continuing therapy. It is recommended that the investigator consult with Lilly (or its designee) before discontinuing therapy for this reason.

Patients discontinuing from the IP prematurely for any reason should complete AE and other follow-up procedures per Section 2.2 (SOA), Section 2.8.2 (Adverse Events) of this addendum, and Section 9.4 (Safety) of the JAHO(e) protocol.

2.7.1.2. Temporary Interruption of Investigational Product

In some circumstances, it may be necessary to temporarily interrupt treatment as a result of AEs or abnormal laboratory values that may have an unclear relationship to IP. For example, IP should be temporarily interrupted if the patient experiences a cardiovascular AE considered to be related to study treatment, is graded as moderate (Grade 2 according to Common Terminology Criteria for Adverse Events Version 3.0), and that does not resolve promptly with supportive

care. Except in cases of emergency, it is recommended that the investigator consult with Lilly (or its designee) before temporarily interrupting therapy for reasons other than those defined in [Table JAHO.2](#).

For the abnormal laboratory findings and clinical events (regardless of relatedness) listed in [Table JAHO.2](#), specific guidance is provided for temporarily interrupting treatment and when treatment may be restarted. Retest frequency and timing of follow-up laboratory tests to monitor the abnormal finding are at the discretion of the investigator. IP that was temporarily interrupted because of an AE or abnormal laboratory value not specifically covered in [Table JAHO.2](#) may be restarted at the discretion of the investigator.

Table JAHO.2. Criteria for Temporary Interruption of Investigational Product

Hold Investigational Product if the Following Laboratory Test Results or Clinical Events Occur:	Investigational Product May Be Resumed When:
WBC count <2000 cells/ μ L ($<2.00 \times 10^3/\mu\text{L}$ or $<2.00 \text{ GI/L}$)	WBC count ≥ 2500 cells/ μ L ($\geq 2.50 \times 10^3/\mu\text{L}$ or $\geq 2.50 \text{ GI/L}$)
ANC <1000 cells/ μ L ($<1.00 \times 10^3/\mu\text{L}$ or $<1.00 \text{ GI/L}$)	ANC ≥ 1200 cells/ μ L ($\geq 1.20 \times 10^3/\mu\text{L}$ or $\geq 1.20 \text{ GI/L}$)
Lymphocyte count <500 cells/ μ L ($<0.50 \times 10^3/\mu\text{L}$ or $<0.50 \text{ GI/L}$)	Lymphocyte count ≥ 750 cells/ μ L ($\geq 0.75 \times 10^3/\mu\text{L}$ or $\geq 0.75 \text{ GI/L}$)
Platelet count <75,000/ μ L ($<75 \times 10^3/\mu\text{L}$ or $<75 \text{ GI/L}$)	Platelet count $\geq 100,000/\mu\text{L}$ ($\geq 100 \times 10^3/\mu\text{L}$ or $\geq 100 \text{ GI/L}$)
eGFR <40 mL/min/1.73 m ² (from serum creatinine) for patients with screening eGFR ≥ 60 mL/min/1.73 m ²	eGFR ≥ 50 mL/min/1.73 m ²
eGFR <30 mL/min/1.73 m ² (from serum creatinine) for patients with screening eGFR ≥ 40 to <60 mL/min/1.73 m ²	eGFR ≥ 40 mL/min/1.73 m ²
ALT or AST $>5 \times \text{ULN}$	ALT and AST return to $<2 \times \text{ULN}$, and IP is not considered to be the cause of enzyme elevation
Hemoglobin <8 g/dL ($<80.0 \text{ g/L}$)	Hemoglobin $\geq 10 \text{ g/dL}$ ($\geq 100.0 \text{ g/L}$)
Symptomatic herpes zoster	All skin lesions have crusted and are resolving
Infection that, in the opinion of the investigator, merits the IP being interrupted	Resolution of infection
Clinical features of VTE (such as deep vein thrombosis or pulmonary embolism) are present ^a	VTE ruled out

Abbreviations: ALT = alanine aminotransferase; ANC = absolute neutrophil count; AST = aspartate aminotransferase; eGFR = estimated glomerular filtration rate; IP = investigational product; ULN = upper limit of normal; VTE = venous thromboembolic event; WBC = white blood cell.

^a Evaluate promptly and institute appropriate treatment. If upon evaluation, VTE is ruled out and no other temporary or permanent discontinuation criteria are met, then IP may be resumed.

Although temporary interruption of IP is not a requirement at times of increased potential risk for VTE (for example, surgery, significant air travel, or other situations involving prolonged immobilization), it is recommended that the investigator follow appropriate VTE prophylaxis guidelines to help manage the VTE risk under these circumstances.

For specific guidance on temporary interruption of IP after the use of a prohibited medication, please refer to Section [2.6.7.2](#) (Prohibited Medications and Procedures).

Lastly, IP should be temporarily interrupted for suicidal ideation or any suicide-related behaviors, as assessed by the following patient responses on the C-SSRS:

- A “yes” answer to Question 4 (Active Suicidal Ideation with Some Intent to Act, Without Specific Plan); **or**
- A “yes” answer to Question 5 (Active Suicidal Ideation with Specific Plan and Intent) on the “Suicidal Ideation” portion of the C-SSRS; **or**
- A “yes” answer to any of the suicide-related behaviors (actual attempt, interrupted attempt, aborted attempt, preparatory act or behavior) on the “Suicidal Behavior” portion of the C-SSRS.

NOTE: Prior to resumption of IP, it is recommended that a patient be assessed by a psychiatrist or appropriately trained professional to assist in deciding whether the subject should remain on IP and, ultimately, continue participation in the study. A patient does not necessarily have to have IP interrupted if he/she has self-injurious behavior that would be classified as non-suicidal self-injurious behavior.

2.7.1.3. Discontinuation of Inadvertently Enrolled Patients

If the Sponsor or investigator identify a patient who did not meet enrollment criteria and was inadvertently enrolled, then the patient should be discontinued from study treatment unless there are extenuating circumstances that make it medically necessary for the patient to continue on study treatment. If the investigator and the Sponsor CRP agree it is medically appropriate to continue, the investigator must obtain documented approval from the Sponsor CRP to allow the inadvertently enrolled patient to continue in the study with or without treatment with IP. Safety follow-up is as outlined in Section 2.2 (SOA), Section 2.8.2 (Adverse Events) of this addendum, and Section 9.4 (Safety) of the JAHO(e) protocol.

2.7.2. Discontinuation from the Study

Patients will be discontinued in the following circumstances:

- enrollment in any other clinical study involving an investigational medicinal product or enrollment in any other type of medical research judged not to be scientifically or medically compatible with this study
- participation in the study needs to be stopped for medical, safety, regulatory, or other reasons consistent with applicable laws, regulations, and GCP
- investigator decision
 - the investigator decides that the patient should be discontinued from the study
 - if the patient, for any reason, requires treatment with another therapeutic agent for AA (not allowed per protocol [Section 2.6.7.2]) that has been demonstrated to be effective for treatment of the study indication, discontinuation from the study occurs prior to introduction of the new agent
- subject decision
 - the patient or the patient’s designee (for example, parents or legal guardian) requests the patient to be withdrawn from the study

Patients discontinuing from the study prematurely for any reason should complete AE and other safety follow-up per Section 2.2 (SOA), Section 2.8.2 (Adverse Events) of this addendum, and Section 9.4 (Safety) of the JAHO(e) protocol.

2.7.3. Lost to Follow-Up

A patient will be considered lost to follow-up if he/she repeatedly fails to return for scheduled visits and is unable to be contacted by the study site. Site personnel are expected to make diligent attempts to contact patients who fail to return for a scheduled visit or were, otherwise, unable to be followed up by the site.

2.8. Study Assessments and Procedures

Section 2.2 lists the SOA, with the study procedures and their timing (including tolerance limits for timing).

Appendix 2 lists the laboratory tests that will be performed for this study.

Unless, otherwise, stated in the subsections below, all samples collected for specified laboratory tests will be destroyed within 60 days of receipt of confirmed test results. Certain samples may be retained for a longer period, if necessary, to comply with applicable laws, regulations, or laboratory certification standards.

2.8.1. Efficacy Assessments

2.8.1.1. Primary Efficacy Assessments

2.8.1.1.1. Severity of Alopecia Tool Score

The SALT uses a visual aid showing the division of the scalp hair into 4 areas with the top constituting 40% of total surface, the posterior/back 24%, right side and left side of scalp 18% each. The percentage of hair loss in each area is determined and is multiplied by the percentage of scalp covered by that area. The total sum of the 4 products of each area will give the SALT score, as developed by the National Alopecia Areata Foundation Working Committee (Oslen et al. 2004). Only terminal hair is included in the SALT; vellus hair or any fine downy hair is not taken into account in the SALT scoring process (Oslen et al. 1999, 2004).

2.8.1.2. Secondary Efficacy Assessments

2.8.1.2.1. Other Clinician-Reported Outcomes

2.8.1.2.1.1. Eyebrow Hair Loss and Eyelash Hair Loss

Lilly has developed 2 single-item ClinRO assessments: ClinRO Measure for Eyebrow Hair Loss™ and ClinRO Measure for Eyelash Hair Loss™. Each of these ClinRO assessments uses a 4-point response scale, ranging from 0 = no hair loss to 3 = severe hair loss (Wyrwich et al. 2020a).

2.8.1.2.2. Alopecia Areata Patient-Reported Outcomes

2.8.1.2.2.1. Patient-Reported Outcomes for Scalp Hair Assessment™

Lilly has developed a novel single-item PRO assessment of the patient's current extent of scalp involvement. It is comprised of 5 category response options: 0 = no missing hair (0% of my

scalp is missing hair; I have a full head of hair); 1 = a limited area (1% to 20% of my scalp is missing hair); 2 = a moderate area (21% to 49% of my scalp is missing hair); 3 = a large area (50% to 94% of my scalp is missing hair); and 4 = Nearly all or all (95% to 100% of my scalp is missing hair) (Wyrwich et al. 2020b).

2.8.1.2.2.2. Patient-Reported Outcomes for Appearance of Eyebrows, Appearance of Eyelashes

Lilly has developed single-item PRO assessments measuring AA signs and symptoms. The PRO Measure for Eyebrows™ and PRO Measure for Eyelashes™ are single-item instruments which use a 4-point response scale, ranging from 0 = no problem to 3 = severe problem (Wyrwich et al. 2020a).

2.8.1.2.2.3. Patient-Reported Outcomes for Body Hair

The Body Hair Symptoms and Impact Questionnaire asks patients about current nasal, beard (male only), and genital hair loss. For each of these areas, patients are asked to assess the amount of hair loss using the categories of “no missing hair,” “a limited amount of hair loss,” “a large amount of hair loss,” or “complete or nearly complete hair loss.” Patients are also asked to rate how bothered they are by the hair loss using a 11-point Numeric Rating Scale of 0 to 10 where 0 is “not at all bothered” and 10 is “worst imaginable for being bothered.”

2.8.1.2.2.4. Patient-Reported Outcomes for Change

Patients will assess their overall impression of change (PGI-C) during the course of therapy. This single-item question assesses their perception of change relative to their baseline status using a 7 Likert-point scale where 1 = very much better, 2 = much better, 3 = a little better, 4 = no change, 5 = a little worse, 6 = much worse, and 7 = very much worse.

2.8.1.2.2.5. Patient-Reported Outcomes for Satisfaction

Treatment satisfaction will be assessed using the single item Patient Global Impression of Satisfaction (PGI-Satisfaction) in which they assess their current satisfaction with the treatment outcome using a 7-point Likert scale where 1 = completely satisfied, 2 = mostly satisfied, 3 = somewhat satisfied, 4 = neither satisfied or dissatisfied, 5 = dissatisfied, 6 = mostly dissatisfied, and 7 = completely dissatisfied.

2.8.1.3. Health Outcomes and Quality-of-Life Measures

The following patient self-reported questionnaires will be administered via an electronic tablet.

2.8.1.3.1. Skindex-16 A for Alopecia Areata

The Skindex-16 has been used to assess the health-related quality of life in patients with skin diseases. The Skindex-16 items' wordings were adapted for use among adults with AA. It is composed of 16 items grouped under 3 domains: Symptoms (4 items), Emotions (7 items), and Functioning (5 items).

2.8.1.3.2. Hospital Anxiety and Depression Scale

The Hospital Anxiety and Depression Scale is a 14-item self-assessment scale that determines the levels of anxiety (7 items) and depression (7 items) that a patient is experiencing over the past week. The Hospital Anxiety and Depression Scale utilizes a 4-point Likert response scale (for example, 0 to 3) for each item, and is intended for ages 12 to 65 years (Zigmond and Snaith 1983; White et al. 1999). Scores for each domain (anxiety and depression) can range from 0 to

21, with higher scores indicating greater anxiety or depression (Zigmond and Snaith 1983; Snaith 2003).

2.8.1.4. Photography

At Screening (Visit 1), photographs of the scalp will be obtained from all patients. Views will include the right lateral, frontal, left lateral, forward tilt, and posterior. Up to 4 additional close-up views will be taken with and without cross-polarization lens of the left and right temporal area, the crown, and a representative patch (when applicable) selected by the physician. At Baseline (Visit 2), photographs of the scalp will be repeated as at the screening visit. All patients will also have photograph of the eyebrows/eyelashes. After baseline, photographs of the scalp and close-up will be repeated as per the SOA. After Baseline, photographs of the eyebrows/eyelashes will be captured only from patients who have AA involvement ($\text{ClinRO} \geq 1$) of those areas at Baseline, as assessed by investigator (see SOA [Section 2.2] and Section 2.8.1.4). Missed photographs after screening will not be considered a protocol violation. Detailed requirements for photography are located in the Photography Manual.

Camera equipment, necessary ancillary materials, and a study-specific photography manual will be provided to all sites by the Sponsor or designee. The photographs will be obtained by trained site personnel under similar lighting conditions and magnifications, and per instructions provided during training and as outlined in the photographic procedure manual.

Photographs are commonly obtained in research investigations of AA and are effective in demonstrating disease presentation at Baseline and clinical response after treatment with baricitinib.

The photographs may be included in the CSR, a regulatory submission package, scientific publications, or in other public dissemination of clinical data to demonstrate disease presentation at Baseline and clinical response after treatment with baricitinib.

Photographs from consenting patients may also be used in advertising and promotional activities including, but not limited to, communication with healthcare professionals/payers, as well as in patient education, speaker programs, and digital/print media messaging.

Patient anonymity will be protected in photographs included in patient education, speaker programs, print media, or any form available to the public. To protect the patient's anonymity, identifiable characteristics of the skin, such as facial birthmarks, or tattoos will be redacted from the final photographs and will not appear in any published version of the photograph. No formal analyses of photographs are planned.

2.8.1.5. Appropriateness of Assessments

The primary clinical and safety assessments in this study are standard, widely used, and generally recognized as reliable, accurate, and relevant.

2.8.2. Adverse Events

Investigators are responsible for monitoring the safety of patients who have entered this study and for alerting Lilly or its designee to any event that seems unusual, even if this event may be considered an unanticipated benefit to the patient.

The Investigator is responsible for the appropriate medical care of patients during the study.

Investigators must document their review of each laboratory safety report.

The Investigator will record all relevant AE/SAE information in the CRF. The Investigator remains responsible for following, through an appropriate health care option, AEs that are: serious or, otherwise, medically important; considered related to the IP or the study; or that caused the patient to discontinue the IP before completing the study. The patient should be followed until the event resolves, stabilizes with appropriate diagnostic evaluation, or is reasonably explained. The frequency of follow-up evaluations of the AE is left to the discretion of the investigator.

Lack of drug effect is not an AE in clinical studies because the purpose of the clinical study is to establish treatment effect.

After the ICF is signed, study site personnel will record, via eCRF, the occurrence and nature of each patient's preexisting conditions, including clinically significant signs and symptoms of the disease under treatment in the study. In addition, site personnel will record any change in the condition(s) and any new conditions as AEs. Investigators should record their assessment of the potential relatedness of each AE to IP, via eCRF.

The investigator will interpret and document whether an AE has a reasonable possibility of being related to study treatment, to a study device, or to a study procedure, taking into account the disease, concomitant treatment, or pathologies. A "reasonable possibility" means that there is a cause-and-effect relationship between the IP, study device, and/or study procedure and the AE. The investigator answers yes/no when making this assessment.

Planned surgeries and nonsurgical interventions should not be reported as AEs unless the underlying medical condition has worsened during the course of the study.

If a patient's IP is discontinued as a result of an AE, study site personnel must report this to Lilly or its designee via eCRF, clarifying, if possible, the circumstances leading to any dosage modifications or discontinuations of treatment.

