2.8.2.1. Serious Adverse Events

An SAE is any AE from this study that results in one of the following outcomes:

- death
- initial or prolonged inpatient hospitalization
- a life-threatening experience (that is, immediate risk of dying)
- persistent or significant disability/incapacity
- congenital anomaly/birth defect

- important medical events that may not be immediately life-threatening or result in death or hospitalization, but may jeopardize the patient or may require intervention to prevent one of the other outcomes listed in the definition above. Examples of such medical events include: allergic bronchospasm requiring intensive treatment in an emergency room or at home; blood dyscrasias or convulsions that do not result in inpatient hospitalization; or the development of drug dependency or drug abuse.

All AEs occurring after signing the ICF are recorded in the eCRF and assessed for seriousness criteria. The SAE reporting to the Sponsor begins after the patient has signed the ICF and has received IP. However, if an SAE occurs after signing the ICF, but prior to receiving IP, the SAE should be reported to the Sponsor, as per SAE-reporting requirements and timelines (see Section 2.8.2) if it is considered reasonably possibly related to study procedure.

Study site personnel must alert Lilly or its designee of any SAE within 24 hours of investigator awareness of the event via a Sponsor-approved method. If alerts are issued via telephone, they are to be immediately followed with official notification on study-specific SAE forms. This 24-hour notification requirement refers to the initial SAE information and all follow-up SAE information. Patients with a serious hepatic AE should have additional data collected using the eCRF.

Pregnancy (during maternal or paternal exposure to IP) does not meet the definition of an AE. However, to fulfill regulatory requirements, any pregnancy should be reported after the SAE process to collect data on the outcome for both the mother and the fetus.

Investigators are not obligated to actively seek AEs or SAEs in subjects once they have discontinued and/or completed the study (the patient disposition eCRF has been completed). However, if the investigator learns of any SAE, including a death, at any time after a subject has been discharged from the study, and he/she considers the event reasonably possibly related to the study treatment or study participation, the investigator must promptly notify Lilly.

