2.8.2.1.1. Suspected Unexpected Serious Adverse Reactions

SUSARs are serious events that are not listed in the IB and that the investigator identifies as related to IP or procedure. United States 21 CFR 312.32 and European Union Clinical Trial Directive 2001/20/EC and the associated detailed guidance or national regulatory requirements in participating countries require the reporting of SUSARs. Lilly has procedures that will be followed for the identification, recording, and expedited reporting of SUSARs that are consistent with global regulations and the associated detailed guidance.

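### The protocol defines a reasonable possibility of relatedness as an actual cause-and-effect relationship; followed literally, this could under-identify SUSARs and some SAEs outside the on-study, post-dose period

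*Protocol*

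**What the plan says.** Protocol section 2.8.2 gives the investigator one causality question: "whether an AE has a reasonable possibility of being related to study treatment, to a study device, or to a study procedure". The next sentence says that a reasonable possibility "means that there is a cause-and-effect relationship between the IP, study device, and/or study procedure and the AE". The response is binary: "The investigator answers yes/no when making this assessment". Earlier in the same section the request is softer: "Investigators should record their assessment of the potential relatedness of each AE to IP, via eCRF".

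Other rules use the investigator's view of relatedness. Section 2.8.2.1.1 describes SUSARs as "serious events that are not listed in the IB and that the investigator identifies as related to IP or procedure". Section 2.8.2.1 requires notification of an SAE learned of after discharge if "he/she considers the event reasonably possibly related to the study treatment or study participation", and uses similar language, tied to study procedure, for an SAE between consent and first dose. Section 2.7.1.2 gives as one example for interrupting treatment that "the patient experiences a cardiovascular AE considered to be related to study treatment".

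**The concern.** A definition overrides the ordinary meaning of the term it defines. Here the term means suspicion and the definition means causation, with no intermediate answer. An investigator who thinks the drug might have contributed, but cannot say that it did, would answer yes to the question and no to the definition. Two conscientious investigators could therefore classify the same case differently, both following the text.

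What is at stake is safety reporting, not estimation. The answer enters the SUSAR definition, two SAE notification rules and part of the follow-up duty. A literal no moves each of these towards less reporting or less follow-up.

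**Working it through.** The plan states no figure on this point and no arithmetic decides it. The check is to set the passages side by side and trace where the answer is used.

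**Step 1: is the wording inconsistent?**

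- Question (2.8.2): is there a reasonable possibility of a relationship? Threshold: possible.
- Definition (2.8.2): a causal relationship exists. Threshold: established. The sentence has no qualifier such as *may*, *possible* or *suspected*.
- eCRF instruction (2.8.2): potential relatedness. Threshold: possible.
- SAE rules before first dose and after discharge (2.8.2.1): reasonably possibly related. Threshold: possible.
- SUSAR section (2.8.2.1.1): the heading speaks of suspected reactions, but the text turns on what the investigator identifies as related. The threshold is inherited from the definition.

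The definition is the only one of these that demands established causation.

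**Step 2: which rules depend on the answer?**

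1. *SUSAR classification (2.8.2.1.1): affected.* An unlisted serious event answered no does not meet the definition as written. The section refers to sponsor procedures for SUSARs but does not say that the sponsor may override the investigator.
2. *SAE after discharge (2.8.2.1): affected.* Notification is required only if the investigator considers the event reasonably possibly related. Patients who continue on marketed product after Week 52 do not need Visit 801 (2.4.1.3), so for them this window can open at Week 52.
3. *SAE after consent, before first dose (2.8.2.1): affected, for procedures only.* The condition is relatedness to a study procedure, so no drug reaction is at issue.
4. *Follow-up of AEs (2.8.2): affected at the margin.* Serious or medically important events, and those that led to stopping treatment, are followed anyway. A no removes only events that are none of these.
5. *SAE on study after first dose (2.8.2.1): not affected.* SAEs are defined by outcome, and every one goes to the sponsor within 24 hours whatever its cause.
6. *AE recording (2.8.2.1) and safety summaries (2.9.5; SAP 4.14.2 and 4.14.2.2): not affected.* All AEs after consent are recorded. Treatment emergence is defined by timing and worsening, seriousness by outcome.

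**Step 3: scale.** The addendum enrolled 20 patients for up to 52 weeks: 20 × 52 = 1,040 patient-weeks, or about 20 patient-years at most. Neither document gives an expected number of unlisted serious events or a rate of equivocal causality judgements, so the number of misclassified events cannot be estimated.

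**The case against.** The strongest reply is that the consequences are limited. A reader might infer that possible reactions drop out of SAE reporting altogether. They do not: the sponsor receives every on-study SAE after first dose within 24 hours, regardless of cause. The sponsor also states that its SUSAR procedures conform to global regulations. Section 2.8.2 tells investigators to report anything unusual, and section 2.8.2.2 collects detail on events of special interest without a relatedness condition. All of this stands. It does not remove the SUSAR point, because the content of the sponsor's procedures is not given and the protocol's definition rests on the investigator. It does mean that actual loss of SUSARs cannot be shown.

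A second reply is that trained specialists will answer the question, not the odd definition. Some will. That possible reactions would be answered no is an inference from the literal text, not a documented practice.

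A third tempting extension is to the treatment-interruption rules. The text does not carry it. Section 2.7.1.2 opens with events whose relationship to treatment is unclear, the cardiovascular case is only an example, and the events in Table JAHO.2 lead to a hold regardless of relatedness. The liver restart condition, "IP is not considered to be the cause of enzyme elevation", has its own wording and does not use the defined term.

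Finally, one might try to size the effect by assuming a relative risk and deriving the share of events caused by the drug. Neither document gives such a risk, or a probability at which the answer should become yes, so the result would only reflect the assumptions.

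**Conclusion.** The inconsistency is real and is visible in two adjacent sentences. The definition sets the bar at established causation while every neighbouring phrase sets it at suspicion. If followed literally, it could under-identify SUSARs, SAEs learned of after discharge, procedure-related SAEs before the first dose, and minor related AEs needing follow-up. Reporting of on-study SAEs after first dose, AE recording and the planned safety tables are unaffected.

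The size is not quantifiable from the documents. The conclusion rests on two assumptions: that at least some investigators apply the definition as written, and that the sponsor's SUSAR procedures do not already correct for it. The protocol confirms neither. This is a wording correction that should be made; it does not threaten the efficacy or safety analyses.

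**What to change.** Replace the defining sentence in section 2.8.2 with wording to this effect: *a reasonable possibility means that there are facts or reasons to suggest a possible cause-and-effect relationship with the investigational product, study device or study procedure; causation need not be established.* State that the same meaning applies to the relatedness wording in sections 2.8.2.1 and 2.8.2.1.1, and notify sites.

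For section 2.7.1.2, the sponsor should reconcile the reference to an unclear relationship and the example that speaks of an event considered related with the definition. How the interruption rule should then read is a clinical matter on which this point takes no position.

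Enrolment is complete, so new wording acts only on later assessments. The sponsor could also ask investigators to revisit any unlisted serious events already answered no; with 20 patients that is a small task.

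The cost is one sentence and a site notice. The downside is somewhat more events marked related and a few more expedited reports.
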